10.6.2.3. Duration of Response

Duration of hematologic response/improvement will be determined only for subjects who achieve a response on treatment. Duration of hematologic response/improvement is defined as the time from the date response/improvement is first observed until the date the subject has a subsequently documented relapse or disease progression as defined by the modified IWG 2006 criteria. Subjects who maintain hematologic response/improvement through the end of the treatment period will be censored at the date of treatment discontinuation or death, whichever occurs first. Duration of response will be assessed for both first response and best response. Duration of hematologic response/improvement for the treatment group will be estimated using KM method.

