In addition to evaluating responses to treatment based on objective criteria, the sponsor, in consultation with the Scientific Steering Committee and Independent Data Monitoring Committee, will also evaluate the quality of each objective response. *Quality of response* will be

assessed based on the magnitude of hematologic and biologic responses observed in individual subjects, with special consideration for response duration. The sponsor may decide to discontinue accrual to one or both cohorts despite observing the required number of objective responses if the responses are not thought to be clinically relevant. For example, if a sufficient quantity of responses is observed, but all responses are transient hematologic improvements that are not thought to convey a meaningful benefit for the subject, the sponsor may choose to not continue enrollment to that cohort in Stage 2. Specific details for what constitutes a *quality response* will be provided in the final Statistical Analysis Plan (SAP).

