6.8.3. International Working Group Modified Response Assessment

Hematologic response or improvement according to criteria modified from that of the International Working Group (IWG) ([Appendix F](#)) is to be assessed following every 2 treatment cycles during the first 6 months of treatment. Subjects who continue treatment will have IWG assessment repeated after every 3 cycles and at treatment discontinuation.

Due to the turnaround time required to obtain results from review of bone marrow aspirate and/or biopsy, peripheral blood smear and cytogenetics, IWG response assessment may be done at any time prior to starting the next cycle of treatment. Decisions regarding dose-modification and treatment continuation following IWG response assessment may be made based on available local assessments, if necessary, ahead of central hematology and bone marrow pathology assessments becoming available. However, after at least 6 cycles of treatment with IP, if central pathology assessment conveys disease progression, the subject must be notified as soon as possible (not later than the next scheduled study visit) to discontinue further study treatment and to schedule the treatment discontinuation visit, as appropriate.

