
Table 8: Definitions of Progressive Disease for Clinical Decisions on Discontinuing Subjects From the Investigational Product and/or From the Study

Category	Progression/Relapse Criteria
Progression in Bone Marrow	
For subjects with:
 
 • Less than 5% blasts at baseline: $\geq 100\%$ increase to $\geq 8\%$ blasts • $\geq 5\%$ blasts at baseline: $\geq 50\%$ increase to $\geq 10\%$ blasts 
Note: A 2nd bone marrow sample should be collected within 4 weeks to confirm progression before discontinuing subjects from treatment.

Progression in RBC Transfusion Requirement ^a	
For subjects not RBC-transfusion-dependent at baseline: Development of RBC transfusion dependence: ≥ 2 RBC transfusions in any 56-day (8-week) period during study treatment.
 
For subjects RBC transfusion-dependent at baseline who do not achieve RBC transfusion independence ≥ 56 days (8 weeks) during study treatment: $> 50\%$ increase in the average RBC transfusion requirement during any 56-day (8-week) period during study treatment compared to the average RBC transfusion requirement in the 56 days (8 weeks) prior to enrollment.

Relapse in RBC Transfusion Requirement ^a	
For subjects RBC transfusion-dependent at baseline who do achieve RBC transfusion independence ≥ 56 days (8 weeks) during study treatment: Relapse is defined as a return to baseline RBC transfusion requirement or worse.

Progression in Platelet Transfusion Requirement	
For subjects not platelet transfusion-dependent at baseline: Development of platelet transfusion dependence: ≥ 2 platelet transfusions in any 56-day (8-week) period during study treatment.
 
For subjects platelet transfusion-dependent at baseline who do not achieve platelet transfusion independence ≥ 56 days (8 weeks) during study treatment: $> 50\%$ increase in platelet transfusion requirement during any 56-day (8-week) period during study treatment compared to the 56-day (8-week) period prior to enrollment.

Relapse in Platelet Transfusion Requirement	
For subjects platelet transfusion-dependent at baseline who achieve platelet transfusion independence ≥ 56 days (8 weeks) during study treatment: Relapse is defined as a return to baseline requirement or worse.

Abbreviations: MDS = myelodysplastic syndrome; RBC = red blood cell.

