Appendix E: Eastern Cooperative Oncology Group (ECOG) Performance Status

Eastern Cooperative Oncology Group (ECOG) Performance Status	
Grade	ECOG
0	Fully active, able to carry on all pre-disease performance without restriction.
1	Restricted in physically strenuous activity but ambulatory and able to carry out work of a light or sedentary nature, eg, light house work, office work.
2	Ambulatory and capable of all self-care but unable to carry out any work activities. Up and about more than 50% of waking hours.
3	Capable of only limited self-care, confined to bed or chair more than 50% of waking hours.
4	Completely disabled. Cannot carry on any self-care. Totally confined to bed or chair.
5	Dead.

Source: Oken MM, Creech RH, Tormey DC, Horton J, Davis TE, McFadden ET, et al. Toxicity and response criteria of the Eastern Cooperative Oncology Group. Am. J. Clin. Oncol. 1982; 5(6):649-55.

Appendix F: Hematologic Response and Improvement According to the International Working Group for MDS – modified

Hematologic Response Modified from IWG Criteria for MDS (Cheson, 2006)	
Category	Response Criteria (responses must last at least 4 weeks)
Complete Remission (CR)	Bone marrow: $\leq 5\%$ myeloblasts with normal maturation of all cell lines ^c Persistent dysplasia will be noted ^a . Peripheral blood ^c Hgb ≥ 11 g/dL Platelets $\geq 100 \times 10^9/L$ Neutrophils $\geq 1.0 \times 10^9/L^b$ Blasts 0%
Partial Remission (PR)	All CR criteria if abnormal before treatment except: – Bone marrow blasts decreased by $\geq 50\%$ over pre-treatment but still $> 5\%$ – Cellularity and morphology not relevant
Marrow CR ^b	Bone marrow: $\leq 5\%$ myeloblasts and decrease by $\geq 50\%$ over pre-treatment ^b Peripheral blood: if HI responses, they will be noted in addition to marrow CR ^b
Stable Disease (SD)	Failure to achieve any objective response (CR, PR, mCR, or HI), but no evidence of disease progression over any 8-week period
Failure	Death during treatment or disease progression characterized by worsening of cytopenias, increase in percentage of bone marrow blasts, or progression to a more advanced MDS FAB subtype than pre-treatment ^d .
Relapse After CR or PR	At least 1 of the following demonstrated by ≥ 2 values, separated by ≥ 2 weeks: – Return to pre-treatment bone marrow blast percentage – Decrement of $\geq 50\%$ from maximum remission/response levels in granulocytes or platelets – Reduction in Hgb concentration by ≥ 1.5 g/dL or transfusion dependence

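### Duration of response censors death in response and any treatment stop without documented relapse, whatever the reason, with no sensitivity analysis

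*Protocol*

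**What the plan says.** Protocol 10.6.2.3 defines duration from the first observation of response "until the date the subject has a subsequently documented relapse or disease progression as defined by the modified IWG 2006 criteria". The censoring sentence is limited to those still in response: subjects who keep their response or improvement to the end of treatment "will be censored at the date of treatment discontinuation or death, whichever occurs first". SAP 10.2.3 repeats both rules. The estimator is Kaplan-Meier. Neither section lists death as an event, uses the reason for stopping, or plans a sensitivity analysis.

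Other parts of the plan bear on this:

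- PFS (Protocol 10.6.2.4, SAP 10.2.4) counts death from any cause as an event.
- Protocol 6.8.3 requires a response assessment at the stop: "Subjects who continue treatment will have IWG assessment repeated after every 3 cycles and at treatment discontinuation". Table 2 lists none at the safety follow-up visits, and the later telephone contacts in 6.14 collect survival, subsequent MDS therapy and AML only.
- Protocol Appendix F sets this condition for relapse after CR or PR: "At least 1 of the following demonstrated by ≥ 2 values, separated by ≥ 2 weeks". The row for relapse after HI has no such condition, and neither does the relapse row of SAP Appendix E.
- Protocol Section 12 includes disease relapse, progressive disease, symptomatic deterioration and physician decision among the reasons for stopping.

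**The concern.** Kaplan-Meier is valid when censoring carries no information about the outcome. Here two kinds of censoring may carry a good deal.

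The first is death in response. Censoring it makes the curve describe how long responses would last if responders did not die, which is longer than the time patients actually spend alive and in response. Protocol 1.4.1 cites a median survival of about 4 to 6 months for higher-risk patients after HMA failure. That figure is not specific to responders, but it means deaths cannot be assumed negligible.

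The second is a stop at which response has probably been lost but has not been documented. A responder stopped for symptomatic deterioration, or at a first poor count after CR or PR, may leave treatment before the second value needed to establish relapse.

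Duration of response is a secondary endpoint, so the immediate stake is a reported durability that looks better than it was.

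**Working it through.** The documents state no duration, event rate or expected number of responders to reproduce. The check is therefore a classification of outcomes under the written rule, followed by an illustration of size.

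**Classification of how a responder's follow-up ends**

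| Ending | Status under 10.6.2.3 and SAP 10.2.3 |
|---|---|
| Relapse or progression documented by IWG criteria | Event |
| Death while in response | Censored at death |
| Stop with no documented relapse, any reason | Censored at the stop |
| First relapse value at the stop after CR or PR, no second value yet | Not addressed |

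The last row depends on which document is used. Under Protocol Appendix F the relapse is unconfirmed; under SAP Appendix E the single value can suffice. Protocol 10.6.2.5 adds a separate requirement of two progression observations at least 8 weeks apart for stable disease, and 10.6.2.3 does not say whether it applies to duration of response.

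Data that could settle many of these cases are already collected: central haematology at the discontinuation and 28-day visits (Protocol 6.7.7), and transfusions until at least 90 days after the last dose (6.8.6).

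**Size under constant hazards (all rates assumed)**

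Let h_d be the monthly hazard of documented relapse or progression. Let h_o be the hazard of response endings that the rule censors: death in response, or true loss that was not documented.

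- Median under the written rule: ln2 / h_d.
- Median with those endings counted: ln2 / (h_d + h_o).
- Ratio: (h_d + h_o) / h_d = 1/(1-s), where s = h_o / (h_d + h_o).

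| s (assumed) | Ratio | A 12-month Kaplan-Meier median becomes |
|---|---|---|
| 0 | 1.00 | 12.0 months |
| 10% | 1/0.9 = 1.11 | 12 × 0.9 = 10.8 months |
| 20% | 1/0.8 = 1.25 | 12 × 0.8 = 9.6 months |
| 30% | 1/0.7 = 1.43 | 12 × 0.7 = 8.4 months |

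**A small constructed example**

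Take eight responders: documented relapse at 2, 5 and 8 months; undocumented stops at 3 and 6; deaths in response at 4 and 10; one ongoing at 12.

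- Written rule: 7/8 × 4/5 × 2/3 = 0.47 at month 8, so the median is 8 months.
- Deaths counted: 7/8 × 5/6 × 4/5 × 2/3 = 0.39 at month 8. The median is still 8 months, but the curve is lower.
- Deaths and undocumented stops counted: 7/8 × 6/7 × 5/6 × 4/5 = 0.50 at month 5, so the median is 5 months.

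With so few subjects, the effect on the median can be nil or large.

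**The case against.** The strongest answer is that the rule is narrower than it looks. A reader who sees only the censoring clause might infer that a responder stopped for relapse is treated as still responding. The documents do not support that. The sentence covers only subjects who maintain response, and documented relapse or progression is an event. An IWG assessment is required at the stop, and for marrow progression Table 8 adds: "A 2nd bone marrow sample should be collected within 4 weeks to confirm progression before discontinuing subjects from treatment". This stands, and it confines the problem to deaths and undocumented loss. The two-value gap is also limited: it arises for relapse after CR or PR under the protocol, not for relapse after HI, and the text is silent on the case instead of ordering censoring.

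Three further objections stand:

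- Stops for lack of efficacy mostly concern non-responders, who are outside this analysis.
- Appendix F describes Failure as "Death during treatment or disease progression characterized by worsening of cytopenias", but Failure is a best-response category. It does not contradict censoring a later death in a responder.
- PFS and OS already report deaths. For the death component, the ratio above compares two different quantities, time to relapse and time to relapse or death. It is not an error in estimating one of them.

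The last point does not remove the issue. A reader will take the reported duration as time spent in response, and the plan neither warns otherwise nor offers the alternative.

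**Conclusion.** The point holds in a limited form. Death in response is censored, stops without documented relapse are censored regardless of reason, and a first unconfirmed relapse value at the stop after CR or PR has no stated handling. To the extent that such endings are real losses of response, the Kaplan-Meier duration is too long. The factor 1/(1-s) rests on constant hazards. The range of 1.11 to 1.43 rests on an assumed s of 10% to 30%, and at s = 0 there is no effect.

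A reader might also infer that the rule could have distorted the choice to continue a cohort, since quality of response is judged "with special consideration for response duration". The documents do not support this. Protocol 4.1.3 describes a judgement on individual subjects' responses and mentions no Kaplan-Meier estimate. The Amendment 4 justification reports that the Phase 2 monotherapy cohorts closed because the response count was not met. The threshold was 3 of 16, so each of those cohorts had at most 2 responders, and the combination arm stopped during the run-in.

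What remains is the reporting of a secondary endpoint in few responders. Severity is minor.

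**What to change.** In Protocol 10.6.2.3 and SAP 10.2.3:

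1. Count death in response as an event.
2. State that central haematology and transfusion data through the 28-day follow-up visit may confirm a relapse first seen at or before discontinuation, dated to the first value.
3. Report two sensitivity analyses: (a) the current rule, and (b) stops recorded as disease relapse, progressive disease or symptomatic deterioration counted as events.

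Analysis (b) belongs among the sensitivity analyses because it accepts unconfirmed investigator judgement in an open-label study.

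The cost is wording and programming on data already collected. The reported duration becomes slightly less favourable.

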10.6.2.4. Progression-free Survival

Progression-free survival (PFS), time to disease progression or death from any cause, will be calculated using date of first dose of IP and the earliest of date of disease progression or date of death, or date of last follow-up for censored subjects. Time to disease progression or death from any cause is defined as the time between first dose and the earliest of disease progression or death from any cause. All subjects will be followed until drop-out, death, or study termination. Drop-out may be due to withdrawal of consent from further data collection or loss to follow-up. Subjects who drop-out or are alive without disease progression at study termination will have their PFS times censored at the time of last contact, as appropriate. The PFS curve will be estimated using Kaplan-Meier (KM) method.

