4.1.5. Follow-up Phase

4.1.5.1. Follow-up in Subjects Receiving CC-486 Monotherapy

All subjects who receive at least one dose of CC-486 in the safety run-in or randomized treatment phase and discontinue treatment for any reason will be followed for at least 28 days after their last dose of CC-486 for the assessment of safety-related parameters (see Section 6.14). After the 28-day period, only SAEs made known to the investigator that are suspected of being related to treatment with CC-486 need to be reported.

A 28-day follow-up visit will be conducted 28 (± 3) days following the last dose of CC-486 or during the final treatment phase study visit (whichever date is later) for assessment of the following safety-related parameters (see Section 6.14).

- Survival,
- AEs including AESI
- Concomitant medications, therapies, and procedures,
- RBC and platelet transfusions,
- New MDS therapies, or
- Disease progression to AML

Subjects in follow-up will then be contacted every 3 months from the date of the 28-day follow-up visit until death, loss-to follow-up, withdrawal of consent to further follow-up, or study closure to collect information related to:

- Survival

- Subsequent MDS-related therapies
- Disease progression to AML.

This will continue until the last active subject completes approximately 12 months of treatment and/or follow-up unless additional follow-up is needed to evaluate time-to-event endpoints (eg, progression-free survival [PFS] and survival). Follow-up contacts will routinely be conducted by telephone unless special circumstances exist (eg, the subject will visit the center for a non-study-related reason).

Females of childbearing potential should avoid becoming pregnant for 90 days after the last dose of IP and male subjects should avoid fathering a child for 90 days after the last dose of IP.

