6.1.15. Bone Marrow Aspirate, Biopsy, and Peripheral Blood Smear

A bone marrow aspirate and biopsy are to be obtained during screening. Whenever a bone marrow sample is collected, a peripheral blood smear is to be prepared as well. Bone marrow and peripheral blood samples are then required following every 2 cycles of treatment during the first 6 treatment cycles (ie, Cycle Day 28 [\pm 14 days]). Subjects who continue beyond Cycle 6 will undergo bone marrow examination following every 3 treatment cycles or when necessary to confirm suspected hematologic response or disease progression, and again upon treatment discontinuation. Samples will be sent for cytogenetic analysis each time a bone marrow sample is collected. Bone marrow biopsy and aspirate are required during screening. Thereafter, only aspiration is necessary unless adequate aspirate cannot be obtained.

Samples will be processed as described in the Central Laboratory Manual and submitted for central review along with any pertinent clinical information. If documentation of MDS diagnosis, WHO/FAB classification and IPSS/IPSS-R risk categorization is available within 2 months of screening, results of central review are not required prior to enrollment of the subject in the study.

Instructions for submission of blood and bone marrow slides/samples, along with relevant clinical information, for central review are provided in the Central Laboratory Manual. Samples and documentation should be prepared and sent to the central reviewer as early in the screening process as possible, and not more than 3 weeks after the subject signs informed consent; this will enable resolution of any issues prior to the subject being enrolled into the study. Therefore, the informed consent process and screening procedures (including bone marrow collection) should be planned with careful consideration for the 28-day screening period to avoid any potential need for re-screening due to exceeding the 28-day limit. Special handling requests such as return of materials to the site will be managed on an individual basis.

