6.8.7. Survival, Progression to AML, and Subsequent MDS Therapies

All subjects discontinued from protocol-prescribed therapy for any reason should undergo treatment discontinuation procedures (Section 6.13) and be followed for survival, disease progression to AML, and subsequent MDS therapies (Section 6.14). Data regarding subsequent therapies, determination of disease progression, and date and cause of death will be recorded in the appropriate CRF.

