6.14. Follow-up

All subjects discontinued from treatment with IP for any reason will be followed for a period of at least 28 days after the last dose of CC-486 (90 days for durvalumab) or until the date of the treatment discontinuation visit, whichever is later. During *Safety Follow-up Visits*, the following assessments will be performed:

- AEs including AESIs (monitored until 28 days after last dose of CC-486 or 90 days after last dose of durvalumab, whichever date is later)
- physical examination
- vital signs
- body weight
- ECOG performance status
- hematology
- serum chemistry (to include amylase and lipase) and thyroid function tests
- pregnancy testing (FCBP only)
- urinalysis
- concomitant medications, therapies and procedures
- transfusion assessment
- subsequent MDS therapies

Females of childbearing potential should avoid becoming pregnant for at least 90 days after the last dose of IP and male subjects should avoid fathering a child for at least 90 days after the last dose of IP. The ICF will address any country-specific requirements, as needed.

All subjects discontinued from protocol-prescribed therapy for any reason will also be contacted by telephone every 3 months (12 weeks \pm 14 days) following the treatment discontinuation visit until the last active subject reaches 12 months of treatment, or until death, loss to follow-up, withdrawal of consent to further follow-up, or study closure to collect information related to:

- survival
- subsequent MDS therapies
- disease progression to AML

The investigator must make every effort to obtain information regarding the subject's follow-up status. All attempts to contact the subject must be documented and appropriate due diligence must be demonstrated before the subject can be considered lost to follow-up (eg, 3 unsuccessful attempts by telephone and one unanswered written attempt sent by certified or traceable post).

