10.2.4. Progression-free Survival

- Progression-free survival (PFS), time to disease progression or death from any cause, will be calculated using date of first dose and the earliest of date of disease progression or date of death, or date of last follow-up for censored subjects.
- Time to disease progression or death from any cause is defined as the time between first dose and the earliest of disease progression or death from any cause.
- All subjects will be followed until drop-out, death, or study termination. Drop-out may be due to withdrawal of consent from further data collection or loss to follow-up. Subjects who drop-out or are alive without disease progression at study termination will have their PFS times censored at the time of last contact, as appropriate.
- The PFS will be estimated using Kaplan-Meier (KM) method.

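### PFS is censored at last contact, although non-AML progression has no scheduled assessment once the post-treatment safety window closes

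*Protocol*

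**What the plan says.** **Censoring rule.** Protocol 10.6.2.4: "Subjects who drop-out or are alive without disease progression at study termination will have their PFS times censored at the time of last contact". SAP 10.2.4 has the same rule: such subjects "will have their PFS times censored at the time of last contact, as appropriate". Neither section names another censoring date, and neither has a rule for subsequent MDS therapy or missed assessments.

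**What is assessed, and until when.**
- IWG response (Protocol 6.8.3): "Subjects who continue treatment will have IWG assessment repeated after every 3 cycles and at treatment discontinuation".
- Marrow beyond Cycle 6 (Protocol 6.1.15): every third cycle, "or when necessary to confirm suspected hematologic response or disease progression, and again upon treatment discontinuation".
- Table 2 has no marrow, IWG response or general disease status entry after the treatment discontinuation visit.
- Haematology continues to the safety follow-up visit: 28 days, or 90 days for durvalumab (Protocol 6.7.7, 6.14, Table 2).
- Transfusions are recorded to 90 days after the last dose (Protocol 6.8.6).
- Progression to AML is monitored until death, loss to follow-up, withdrawal or study closure (Protocol 6.7.2, 11.7.1).

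**Long-term follow-up.** Protocol 4.1.5.1: "Subjects in follow-up will then be contacted every 3 months from the date of the 28-day follow-up visit until death" or another stated end of follow-up. Protocol 6.14: "All subjects discontinued from protocol-prescribed therapy for any reason will also be contacted by telephone every 3 months". The items listed are survival, subsequent MDS therapy and AML. Protocol 6.8.7 likewise has discontinued subjects "be followed for survival, disease progression to AML, and subsequent MDS therapies". Sections 4.1.5.1 and 4.1.5.2 name PFS as a reason to extend this follow-up, but schedule no assessment for it.

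**Contrast.** Protocol 10.6.2.3 and SAP 10.2.3 censor duration of response at treatment discontinuation or death, not at last contact.

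**The concern.** Under Protocol Appendix F, progression includes a rise in marrow blasts, worsening cytopenias and transfusion need. None of these has a scheduled assessment during the three-monthly contacts. A subject who stops for toxicity, physician decision or another non-progression reason therefore stays in the PFS risk set as event-free until the last contact, AML or death, even while on a new MDS therapy. From the end of the safety window, the curve describes freedom from AML or death rather than PFS as defined.

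The direction does not depend on a model. A missed progression can only move a subject's event later or turn it into a censored time. Each PFS curve describes one cohort with no randomised contrast planned on PFS, so no comparator offsets the bias.

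**Working it through.** **1. Plan's own figures.** The documents state no PFS median, event count or drop-out rate, so there is no PFS figure to reproduce. The one design calculation is the Simon rule for ORR (stop at 2 or fewer of 16; reject at 8 or more of 41). Summing P(X1 = x | 16) × P(X2 ≥ 8 − x | 25) over x ≥ 3 gives type I error 0.0995 at p = 0.125 and power 0.801 at p = 0.27. This matches the stated 10% and 80%, and it does not use PFS.

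**2. One subject.** Suppose treatment stops at month 4 and the last contact is at month 12. The rule credits 12 months, 8 of them after stopping. With the SAP's 30.4167 days per month, haematology covers 28/30.4167 = 0.92 month after the stop and transfusion records cover 90/30.4167 = 2.96 months. The remaining 8 − 2.96 = 5.04 months have no scheduled assessment of non-AML progression.

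**3. A cohort (all inputs assumed).** Take independent exponential times with medians m_p (progression), m_s (stopping for another reason) and m_d (death). The hazards are p, s, d = ln 2 / median. Progression is visible until w months after stopping.

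- True PFS: S(t) = exp[−(p + d)t], with median 1/(1/m_p + 1/m_d).
- As written, for t > w: S(t) = exp(−dt − pw) × [s/(p+s) + p/(p+s) × exp(−(p+s)(t − w))].

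Example with (m_p, m_s, m_d) = (6, 3, 15), t = 12, w = 0.92:
- True: 2^−(12/6 + 12/15) = 2^−2.8 = 0.144.
- As written: 2^−0.8 × 2^−0.153 × [2/3 + 1/3 × 2^−5.54] = 0.574 × 0.899 × 0.674 = 0.348.
- With w = 2.96: 0.574 × 0.710 × 0.681 = 0.278.

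| m_p, m_s, m_d (months) | Median true | Median, w = 28 d | Median, w = 90 d | 12-month PFS true | w = 28 d | w = 90 d |
|---|---|---|---|---|---|---|
| 6, 3, 5 | 2.7 | 2.9 (+7%) | 2.7 (0%) | 5% | 11% | 9% |
| 4, 6, 9 | 2.8 | 2.9 (+6%) | 2.8 (0%) | 5% | 14% | 11% |
| 6, 3, 15 | 4.3 | 5.8 (+36%) | 4.5 (+4%) | 14% | 35% | 28% |
| 8, 3, 15 | 5.2 | 7.4 (+42%) | 5.7 (+9%) | 20% | 39% | 33% |

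With m_d = 5, m_p from 4 to 8 and m_s from 3 to 6, the 28-day inflation of the median is 3% to 7%. The value m_d = 5 sits inside the 4-6 months that Protocol 1.4.1 cites for higher-risk disease after HMA failure.

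A separate simulation used no visibility after stopping, m_p of 4 to 9, m_s of 6 to 24, m_d of 6 to 18, and follow-up uniform over 12 to 51 months (39 months' accrual plus 12). It raised the median by 0.1 to 2.0 months and 12-month PFS by 2 to 19 percentage points.

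**4. Does moving the censoring date suffice?** Not alone. If only subjects who remain event-free are censored at the last assessment, those who later die keep their unassessed time and count at death. For (6, 3, 15) with w = 0.92, the simulated median is 4.8 with follow-up over 12 to 36 months and 5.0 over 12 to 51 months, against 5.8 as written and 4.3 true. In the second case (5.0 − 4.3)/(5.8 − 4.3), or nearly half the excess, remains. The median returns to 4.3 only when follow-up is also cut at the last assessment for later deaths, and then only because stopping was assumed independent of progression.

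**The case against.** Several counter-arguments have weight.

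- **Follow-up is not empty after treatment stops.** A reader might infer that only survival, AML and later therapy are collected from the day of stopping. The documents do not support that. Safety-visit haematology and 90 days of transfusion data bear on progression, and AML is followed throughout. The gap is non-AML progression after that window. The 90-day columns are an upper bound on visibility, because transfusion need is only one criterion.
- **Short survival limits the effect.** With the survival the protocol cites for higher-risk disease, the median hardly moves. Lower-risk subjects are also eligible (Protocol 7.1), so longer survival cannot be excluded. A 3-month median time to a non-progression stop has no source in the documents, which recommend at least 6 cycles. The large figures need both early stopping and long survival.
- **The wording leaves room.** The SAP's "PFS times censored at the time of last contact, as appropriate" allows judgement, and Protocol 6.8.7 has a determination of disease progression entered in the CRF after discontinuation. But no alternative date is defined and no assessment is scheduled behind that entry.
- **Censoring at the last assessment has its own bias.** Stop reasons in Protocol Section 12 include symptomatic deterioration and lack of efficacy. Censoring at such stops may be informative, possibly also upward. This stands, and is why both versions should be shown.
- **PFS is secondary.** It is estimated by Kaplan-Meier with no hypothesis attached. This limits the importance of the point but does not make the curve correct.

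**Conclusion.** The point holds. The PFS censoring date runs past the last scheduled assessment that could show non-AML progression, so PFS is biased upward. The distortion is mainly in the tail: 12-month PFS was inflated in every scenario run, while the median ranged from unchanged to about 40% too high.

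A reader might infer one general percentage for the inflation. The documents do not support one: they contain no PFS inputs, and the result depends on assumed survival, stopping and visibility. A reader might also infer that the trial's go/no-go decision is affected. It is not, since that rests on ORR alone. The calculations assume independent exponential times, and the window w treats all forms of progression, including AML, as equally visible. AML is in fact followed beyond w, which makes the true bias smaller than shown.

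**What to change.** In Protocol 10.6.2.4 and SAP 10.2.4:

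1. Replace last contact with the date of the last disease assessment able to show progression: marrow or IWG assessment, safety-visit haematology, or the transfusion record up to 90 days after the last dose.
2. State how a death or AML event long after that assessment is handled, for example by censoring at the last adequate assessment when the event falls beyond a stated gap. Without this, much of the bias remains.
3. State how PFS is handled when a subsequent MDS therapy starts.
4. Report last-contact censoring, with all deaths and AML counted as events, as a sensitivity analysis. Note that the main version assumes stopping is not informative.

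The cost is SAP wording and one derivation, with no new data. The downside is more censoring and a less favourable curve.
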